13. STATISTICAL CONSIDERATIONS

13.1 Study Design/Endpoints

We have designed a single stage phase II, three-arm study for the primary endpoint of progression-free rate at 12 weeks. Participants will be stratified among three-arms based upon participant diagnosis. Arm A will consist of leiomyosarcoma participants. Arm B will consist of liposarcoma participants. Arm C will consist of undifferentiated pleomorphic sarcoma/other sarcomas.

The primary endpoint is the 12-week progression-free survival. The progression-free survival is defined as the absence of disease progression at 12 weeks from study enrollment. Participants without stable disease or complete or partial response, with deaths of any cause within 12 weeks, with progression within 12 weeks, or without confirmatory scans at 12 weeks' post baseline evaluation will be counted as failures. We will enroll 19 participants in each arm following a single stage approach.

Toxicity is an important secondary endpoint. With 19 participants in each arm, there is at least 86% probability of observing one or more toxicities with a true rate as low as 10%. With 19 treated participants in each arm, the maximum width of a 90% two-sided confidence interval for any estimated adverse event proportion is $\pm 20\%$.

Progression-free survival (PFS) and overall survival (OS) of participants receiving combination therapy will be described using the method of Kaplan and Meier and 90% confidence intervals for PFS and OS will be reported.

NOTE: With Protocol Version 15MAY2024, further long-term follow-up is being terminated.

13.2 Sample Size, Accrual Rate and Study Duration

Arm A (Leiomyosarcoma)

We will assess the progression-free rate at 12 weeks (null: 30%, alternative: 60%). We will need to observe at least 9 participants absent of disease progression out of 19 participants to accept the treatment. The overall power for the progression-free rate at 12 weeks is 91% using the exact binomial distribution. The operating characteristics of this design are calculated using a one-sided exact test with 10% type I error.

Arm B (Liposarcoma)

We will assess the progression-free rate at 12 weeks (null: 30%, alternative: 60%). We will need to observe at least 9 participants absent of disease progression out of 19 participants to accept the treatment. The overall power for the progression-free rate at 12 weeks is 91% using the exact binomial distribution. The operating characteristics of this design are calculated using a one-sided exact test with 10% type I error.

Arm C (Undifferentiated Pleomorphic Sarcoma/Other Sarcomas)

We will assess the progression-free rate at 12 weeks (null: 30%, alternative: 60%). We will need to observe at least 9 participants absent of disease progression out of 19 participants to accept the treatment. The overall power for the progression-free rate at 12 weeks is 91% using the exact binomial distribution. The operating characteristics of this design are calculated using a one-sided exact test with 10% type I error. Additionally, response to individual sarcomas histologic subtypes will be reported descriptively.

Table 10. Accrual Targets

Accrual Targets				
Ethnic Category	Sex/Gender			
	Females		Males	Total
Hispanic or Latino	1	+	1	= 2
Not Hispanic or Latino	27	+	28	= 55
Ethnic Category: Total of all participants	28	+	29	= 57
Racial Category				
American Indian or Alaskan Native	1	+	1	= 2
Asian	1	+	1	= 2
Black or African American	1	+	1	= 2
Native Hawaiian or other Pacific Islander	1	+	1	= 2
White	24	+	25	= 49
Racial Category: Total of all participants	28	+	29	= 57

13.3 Stratification Factors

There are no planned stratification factors within each cohort of this study.

13.4 Interim Monitoring Plan

No planned interim efficacy analysis. This is a single stage study in each of three liposarcoma, leiomyosarcoma, and undifferentiated pleomorphic sarcoma cohorts/other sarcomas.

13.5 Analysis Plan

Participants' demographic characteristics including age, gender, and race will be analyzed, with categorical variables summarized in frequency tables while continuous variables will be summarized using mean (\pm s.d.) and median (range). The student t-test/Wilcoxon test and ANOVA/Kruskal-Wallis test [Woolson and Clarke, 2000] will be used to compare continuous variables between different participant groups. The chi-square test or the Fisher's exact test [Woolson and Calrke, 2000] will be applied to assess the association between two categorical variables.

13.6 Analysis of Primary Endpoints

For the analysis of the primary endpoint (PFS_{12 weeks}), we will provide respective point estimate along with 90% confidence interval for each of the combinations. PFS is defined as the time from baseline disease evaluation to either disease progression as defined by RECIST or death from any cause, whichever occurs first. For events that have not occurred by the time of data analysis, times will be censored at the last contact at which the participant was known to be progression-free. Log-rank test (Mantel, 1966) will be performed to test the difference in survival between groups. Regression analyses will be conducted of survival data based on the Cox proportional hazards model (Cox, 1972). The proportional hazards assumption will be evaluated graphically and analytically, and regression diagnostics (e.g., martingale and Shoenfeld residuals) will be examined to ensure that the models are appropriate.

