5. TREATMENT PLAN

5.1 Treatment Regimen

This is a non-randomized phase 2 study of eribulin in combination with pembrolizumab for the treatment of liposarcomas, leiomyosarcoma, and undifferentiated pleomorphic sarcomas. Eligible participants with liposarcoma, leiomyosarcoma, or undifferentiated pleomorphic sarcoma/other sarcomas will be divided into three separate cohorts by histologic subtype. Arm A: Leiomyosarcoma, Arm B: Liposarcoma, and Arm C: Undifferentiated Pleomorphic Sarcoma/other sarcomas. A treatment cycle will be defined as 21 consecutive days. Treatment will be eribulin 1.4 mg/m² administered on Day 1 and on Day 8 of each 21-day cycle, plus pembrolizumab 200mg administered on Day 1, of each 21-day cycle. If treatment is delayed, protocol required restaging assessments will remain on-schedule. Eribulin and pembrolizumab will be administered on an outpatient basis. Reportable adverse events and potential risks are described in Section 7. Appropriate dose modifications are described in Section 6. No investigational or commercial agents or therapies other than those described below may be administered with the intent to treat the participant's malignancy.

Treatment regimen is described in Table 1.

Table 1 Treatment Regimen.

Regimen Description					
Agent	Premedication; Precautions	Dose	Route*	Schedule	Cycle Length
Eribulin	No routine premedication required, addition of 4 to 8mg of dexamethasone and/or 8 to 16mg of Zofran allowed for nausea as per institutional standard ⁺	1.4mg/m ²	IV, infuse over 2 to 5 min, may be administered per institutional standard	Day 1 and Day 8	21 days (3 weeks)
Pembrolizumab	Not routinely necessary unless prior infusion reaction. ⁺	200mg	IV infuse over ~ 30 min as per institutional standard, infuse prior to starting eribulin infusion, per institutional standard	Day 1	
* Dose reductions may be made as per Tables 3.1-4.9. Further details about dose reductions can					

be found in Section 6.

+Pre-medications can be administered prior to pembrolizumab. Pre-medications for pembrolizumab and eribulin may be administered per institutional standards.

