5.8 Criteria to Resume Treatment after a pembrolizumab related iAE

Management of adverse events is summarized in section 6 and may include holding of pembrolizumab, and/or the use of steroids for the management of immune related AEs. If pembrolizumab is held for toxicity, participants are permitted to continue protocol therapy with eribulin. Eribulin can be continued during corticosteroid treatment.

If drug administration is held until the next scheduled time point, please continue to count weeks/doses. If participants must be delayed due to toxicity, all assessments can be obtained with the modified treatment dose schedule as noted in this section.

Pembrolizumab may be interrupted for situations other than treatment-related AEs such as medical / surgical events or logistical reasons not related to study therapy. Participants should be placed back on study therapy within 8 weeks of the scheduled interruption, unless otherwise discussed with the Sponsor. The reason for interruption should be documented in the participant's study record.

Restarting pembrolizumab may be considered in participants who experience grade 2 events and some grade 3 events (skin rash and thyroiditis). Because of this, stopping treatment and starting steroids earlier, as per section 6, to obtain resolution with the possibility for restarting rather than waiting for higher grade events is encouraged.

For non-autoimmune or non-inflammatory events, participants may resume treatment with study drug when the drug-related AE(s) resolves to Grade ≤ 1 or the baseline value, with the following exceptions:

- Evaluation to exclude any additional immune mediated events (endocrine, GI, and liver / pancreas function) as clinically indicated must be made prior to restarting. [SEP]
- Non-drug-related toxicity including hepatic, pulmonary toxicity, diarrhea, or colitis, must have resolved to baseline before treatment is resumed. [SEP] If the criteria to resume treatment are met, the participant should restart treatment no sooner than the next scheduled time point per protocol. However, if the treatment is delayed past the next scheduled time point per protocol, the treatment should resume at the earliest convenient point [SEP] that is within the five-week delay period.

For participants treated with corticosteroids:

For participants treated with high dose steroids with pembrolizumab, toxicity must resolve to baseline within 8 weeks of treatment.

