10. STUDY CALENDAR

Baseline evaluations are to be conducted within 2 weeks (14 days) prior to start of protocol therapy. Baseline assessments include: hematology panel, serum chemistry/LFT panel, pregnancy test, EKG, thyroid studies, performance status, HIV, Hep B, C testing, physical examination, medical history, concurrent medications evaluations, vital signs, demographics, weight, and height. Scans and x-rays should be done ≤ 2 weeks prior to the start of therapy. CBC and serum chemistries must be obtained on Cycle 1 Day 1 to determine safety of study drug administration as per section 5.2.1.. In the event that the participant’s condition is deteriorating, laboratory evaluations should be repeated within 48 hours prior to initiation of the next cycle of therapy.

Assessments must be performed prior to administration of any study agent. Study assessments and agents should be administered within ± 3 days of the protocol-specified date, unless otherwise noted. Please reference section 6.1 table 2 for window restrictions due to eribulin dosing.

NOTE: With Protocol Version 15MAY2024, further long-term follow-up is being terminated.

- d: TSH, free T4, obtained during study screening, then Cycle 3 Day 1, and then every 6-8 weeks thereafter.
- e: Assessments done prior to drug administration within 48 hours.
- f: Repeat screening tests if >2 weeks of 14 days from Cycle 1 Day 1.
- h: Initial imaging CT or MRI Tumor measurements should be within 2 weeks from Cycle 1 Day 1.
- i: Including specific focus on immune-related adverse events.
- j: Schedule post Cycle 4 will repeat as per Cycles 1 -4, with the exception of pre/post tumor biopsy and correlative studies. Participants will continue to receive the study treatment each cycle (Day 1, Day 8) until progression or discontinuation with physical exam and laboratory evaluation prior to each drug administration, and repeat imaging (same as baseline) every 6 weeks/2 cycles for up to two years of treatment, or 35 cycles. For participants beyond Cycle 8, repeat imaging may be obtained every 12 weeks/4 cycles. If patients stop eribulin for treatment related effects and are continuing pembrolizumab alone, day 8 assessments will not be required.

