11. MEASUREMENT OF EFFECT

11.1 Antitumor Effect – Solid Tumors

For the purposes of this study, participants should be re-evaluated for response every 6 weeks (+/- 3 days). In addition to a baseline scan, confirmatory scans should also be obtained at 6 weeks (+/- 3 days) following initial documentation of objective response. For participants who are beyond Cycle 8, restaging scans may be obtained at 12 week intervals (+/- 3 days).

Response and progression will be evaluated in this study using the new international criteria proposed by the Response Evaluation Criteria in Solid Tumors (RECIST) guideline (version 1.1)¹. Changes in the largest diameter (unidimensional measurement) of the tumor lesions and the shortest diameter in the case of malignant lymph nodes are used in the RECIST criteria.

All participants who receive at least one dose of eribulin and pembrolizumab will be included in the toxicity analysis. This includes participants who receive study drug and are ultimately deemed ineligible to measure response.

Pembrolizumab, like other immunotherapeutic agents, may produce antitumor effects by inducing or potentiating the endogenous cancer-specific immune response. The response to treatment with immunotherapy may differ from traditional cytotoxic agents. Responses may be seen after the typical time course predicted with cytotoxic agents. Additionally, responses may be seen after initial tumor increase in size or burden or even the appearance of new lesions. To account for these potential response patterns, imaging data will be collected to potentially evaluate for response by irRECIST, in addition to standard RECIST 1.1 assessments. On prior sarcoma immunotherapy trials, such as SARC028, there has not been a significant difference between responses per RECIST 1.1 or irRECIST. Comparison of RECIST 1.1 and irRECIST on this trial may help to clarify if immune response patterns are seen in sarcoma participant's receiving immunotherapy. Clinical decision-making regarding progressive disease and trial discontinuation will still utilize RECIST 1.1.

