11.1.6 Overall Survival, Progression-Free Survival, Time-to-Progression

Overall Survival: Overall Survival (OS) is defined as the time from randomization (or registration) to death due to any cause, or censored at date last known alive.

Progression-Free Survival: Progression-Free Survival (PFS) is defined as the time from randomization (or registration) to the earlier of progression or death due to any cause. Participants alive without disease progression are censored at date of last disease evaluation.

Time to Progression: Time to Progression (TTP) is defined as the time from randomization (or registration) to progression, or censored at date of last disease evaluation for those without progression reported.

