13.7 Analysis of Secondary Endpoints

OS is defined as the time from treatment onset to death. For events that have not occurred by the time of data analysis, times will be censored at the last contact at which the participant was known to be progression-free for PFS, or the last time the participant was known to be alive for OS. PFS and OS will be estimated using the Kaplan-Meier method (Kaplan, 1958) and 90% confidence intervals for PFS and OS will be reported. Log-rank test (Mantel, 1966) will be performed to test the difference in survival between groups. Regression analyses of survival data based on the Cox proportional hazards model (Cox, 1972) will be conducted on PFS or OS. The proportional hazards assumption will be evaluated graphically and analytically, and regression diagnostics (e.g., martingale and Shoenfeld residuals) will be examined to ensure that the models are appropriate.

NOTE: With Protocol Version 15MAY2024, further long-term follow-up is being terminated.

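### PFS has two distinct origins under three labels, neither tied to the scan calendar, so the plan does not settle how progression first seen on the week-12 scan is scored

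*Combined protocol and SAP*

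**What the plan says.** Three sections start the PFS clock, and they do not agree.

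- Section 13.1, for the primary endpoint: "The progression-free survival is defined as the absence of disease progression at 12 weeks from study enrollment". The same paragraph also requires a scan 12 weeks after the baseline evaluation, and a participant without one is a failure.
- Section 13.6, for the primary analysis: "PFS is defined as the time from baseline disease evaluation to either disease progression as defined by RECIST or death from any cause".
- Section 11.1.6: "Progression-Free Survival (PFS) is defined as the time from randomization (or registration) to the earlier of progression or death due to any cause". Nobody is randomized, so this means registration.

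Treatment start appears as an origin only for overall survival, in 13.7: "OS is defined as the time from treatment onset to death". Section 11.1.6 starts overall survival at registration.

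The imaging calendar runs on treatment. Section 1.1 places tumor assessment after every two 21-day cycles, and 11.1 sets a 6-week interval with a window of 3 days either way. For the baseline scan, section 10 says "Initial imaging CT or MRI Tumor measurements should be within 2 weeks from Cycle 1 Day 1", whereas 11.1.3 allows up to 4 weeks before treatment. Section 11.1 dates progression to the day it was first observed.

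Section 13.1 lists the failures: participants with none of CR, PR or SD (no time point is attached), death or progression within 12 weeks, or no 12-week scan. Section 13.2 applies the decision rule to the resulting count: at least 9 of 19 per arm, 30% against 60%, one-sided exact test at 10%.

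On dose delays, 5.1 says "If treatment is delayed, protocol required restaging assessments will remain on-schedule", while 5.8 says that "all assessments can be obtained with the modified treatment dose schedule as noted in this section".

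**The concern.** A 12-week endpoint read from a 12-week scan depends on which side of day 84 that scan falls. If the clock starts before treatment and the scans are timed from treatment, the scan meant to establish 12-week status usually carries a date later than 12 weeks. A participant whose progression is first seen there then has a PFS time above 84 days. Under the definition in 13.6, or a Kaplan-Meier estimate at day 84, that participant is event-free at 12 weeks. What is measured then moves towards status at the week-6 scan, while the 9-of-19 rule was calibrated to a 12-week rate.

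This matters because each arm's go/no-go decision rests on a count out of 19, where a few reclassified participants are enough to cross the threshold. Two analysts following different sections could reach opposite conclusions for the same arm.

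**Working it through.** **Inputs from the documents.** n = 19, cut-off 9, rates 30% and 60% (13.2); scans after every two 21-day cycles (1.1), 6 weeks ± 3 days (11.1); baseline imaging at most 14 days (section 10) or 28 days (11.1.3) before treatment; progression dated when first observed (11.1).

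**Assumptions not in the documents.** PFS is exponential; the true progression-free rate at the week-12 scan is 30%; progression is dated at the detecting scan; scan days and lags are spread evenly over whole days in their ranges.

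**Step 1: the plan's own figure.** P(X ≥ 9 | 19, 0.60) = 0.912, which reproduces the stated 91%. P(X ≥ 9 | 19, 0.30) = 0.084, within the nominal 10%. A cut-off of 8 would give type I error 0.182, and a cut-off of 10 would give power 0.814.

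**Step 2: where the second restaging falls.** 4 × 21 = 84, so it is due on day 81 to 87 from Cycle 1 Day 1. If the origin is L days earlier, it falls on day 81 + L to 87 + L:

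- L = 0: day 81 to 87
- L = 7: day 88 to 94
- L = 14: day 95 to 101
- L = 28 (only under 11.1.3): day 109 to 115

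Days 81 to 83 are possible when L is 0 to 2. From L = 4 every in-window scan is after day 84. The lag from registration to Cycle 1 Day 1 is not limited in the documents.

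**Step 3: one participant under each rule.** Take SD at week 6 and progression first seen on day 86 of the chosen clock.

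- 13.6, or Kaplan-Meier at day 84: event-free at 12 weeks.
- 13.1, progression within 12 weeks: not met.
- 13.1, none of CR, PR or SD: a failure if this means status at week 12; not a failure if it means best response.

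**Step 4: conditional size.** Let f be the share of week-6-to-12 progressions that are dated after day 84 and so counted as success. The apparent rate is p = S(84) + f × [S(42) − S(84)], with S(84) = 0.30 and S(42) = √0.30 = 0.548, so p = 0.30 + 0.248f.

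| f | p | P(X ≥ 9 of 19) |
|---|---|---|
| 0 (status reading) | 0.300 | 0.084 |
| 0.10 | 0.325 | 0.128 |
| 0.25 | 0.362 | 0.217 |
| 0.50 | 0.424 | 0.414 |
| 1 | 0.548 | 0.810 |

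For each origin, f is the proportion of scan-day and lag combinations dated after day 84. The last two columns come from simulating event times and scan days together; the formula agrees to within about one percentage point.

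| Origin | f | p | P(X ≥ 9 of 19) |
|---|---|---|---|
| Cycle 1 Day 1 | 3/7 = 0.43 | 0.41 | 36% |
| Registration 0–7 days earlier (assumed lag) | 46/56 = 0.82 | 0.50 | 69% |
| Baseline scan 0–14 days earlier | 95/105 = 0.90 | 0.52 | 75% |
| Baseline scan 4–14 days earlier (assumed lag) | 1 | 0.55 | 81% |

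If 25% to 50% of the week-6-to-12 failures are dated earlier, by death or symptoms, the simulated figure on the 0–14 day clock is about 60% to 43%. At a true rate of 60%, power only rises, from 0.912 to 0.999 at f = 1, so this error runs towards accepting the treatment.

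**Step 5: the opposite error.** Section 13.1 anchors the required scan at 12 weeks after the baseline evaluation. With a 14-day lag that is day 84 − 14 = 70 from Cycle 1 Day 1, when no scan is scheduled. Read literally, a participant scanned on schedule would fail.

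**The case against.** The strongest reply is that 13.1 already solves the problem. It fails anyone with none of CR, PR or SD, and the sentence also calls for a 12-week scan. The natural reading is status at that scan, which makes progression seen there a failure whatever its date. Section 1.3.1 is built the same way, with clinical benefit defined as CR, PR or SD at 12 weeks. The decision rule in 13.2 is a binary count with an exact test, and 13.6 contains no decision rule. On this view the 13.6 clock never touches the go/no-go decision.

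Much of this stands. The status reading is reasonable and preserves the planned operating characteristics. But the clause has no time point. Section 13.6 is headed as the analysis of the primary endpoint, defines it as a censored time, names no estimator for the 12-week figure, and goes on to log-rank and Cox. Sections 13.1 and 13.7 specify Kaplan-Meier for PFS. A day-84 Kaplan-Meier estimate is therefore a plausible way to carry out the plan.

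Other limits are fair. Sections 2.4 and 2.7 call the 30% a PFS rate at 12 weeks, without tying it to the restaging scan. The 0–7 and 4–14 day lags are assumed. No section gives Cycle 1 Day 1 as the PFS origin. The literal failure of on-schedule participants in Step 5 is a strained reading, because the phrase may simply name the scheduled restaging. The sentence in 5.8 is permissive and general, so 5.1 may be meant to govern scans.

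**Conclusion.** The concern holds as an unresolved conflict in the definition of the primary endpoint. There are two distinct PFS origins under three labels: enrollment or registration (13.1, 11.1.6) and baseline disease evaluation (13.6, and the scan anchor in 13.1). Neither is the origin of the imaging calendar, and no rule assigns a scan to week 12 or says how progression on it is scored.

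The size depends on the reading. On the status reading, type I error is 8.4% and power 91%, as planned. On the date-based reading, the chance of accepting an arm with a true 30% rate could be about 36% to 75%, and 81% at worst. It is about 60% to 43% on the 0–14 day clock if a quarter to a half of the later failures are dated earlier. All of these rest on exponential PFS and the dating and lag assumptions above. Even f = 0.10 gives 12.8%, above the nominal 10%.

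A reader might infer three stronger things that the documents do not support:

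- That there are three separate origins. Enrollment and registration are in substance one.
- That the week-12 scan always falls on or after day 84. The window allows days 81 to 83.
- That an inactive regimen would usually pass. That requires the date-based reading to govern the count in 13.2, which no section says.

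Because the choice can reverse the decision in any of the three arms, the text should be settled before the endpoint is analyzed.

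**What to change.** - Use one PFS origin in 11.1.6, 13.1 and 13.6. Cycle 1 Day 1 is one option, since the scans already run from it; what matters is that the three sections agree.
- Define the primary endpoint as status at the scheduled week-12 restaging, with a stated window. RECIST progression at or before that scan, or death by then, is a failure whatever its calendar day.
- Remove from 13.1 the requirement that ties the scan to 12 weeks after the baseline evaluation, and use the same window for the missing-scan rule.
- Name the exact binomial proportion in 13.6 as the primary estimator, to match 13.2, and keep Kaplan-Meier for the PFS curve.
- Reconcile 5.1 with 5.8 on whether efficacy scans shift with dose delays. Deleting the 5.8 sentence outright could affect other assessments that it covers.
- Reconcile the 2-week limit for baseline imaging in section 10 with the 4-week limit in 11.1.3.

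The cost is protocol and SAP wording. No extra scans or participants are needed, and with progression on the week-12 scan scored as failure the stated design is kept (type I error 0.084, power 0.912).

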13.9.2 Evaluation of the Primary Efficacy Endpoint

All analyses will be intent-to-treat analyses. All the analyses will be conducted separately by each cohort, leiomyosarcoma, liposarcoma, and undifferentiated pleomorphic sarcoma/other sarcomas.

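### Section 13.6 analyses the primary endpoint as a censored time, which contradicts the missing-scan-is-failure count and exact 9-of-19 rule in 13.1 and 13.2, so the reported 12-week rate can exceed the rate on which the decision rests.

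*Combined protocol and SAP*

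**What the plan says.** Section 13.1 says that the primary endpoint "is defined as the absence of disease progression at 12 weeks from study enrollment". Deaths and progressions within 12 weeks are failures, and participants "without confirmatory scans at 12 weeks' post baseline evaluation will be counted as failures". Section 13.2 gives every cohort the same design: null 30%, alternative 60%, 19 participants, and acceptance if at least 9 are free of progression, with stated power of 91%. It adds: "The operating characteristics of this design are calculated using a one-sided exact test with 10% type I error".

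Section 13.6 is headed as the primary-endpoint analysis and opens with the 12-week endpoint. It asks for a point estimate with a 90% confidence interval, without naming a method. It then defines PFS as a time, and for participants without an event "times will be censored at the last contact at which the participant was known to be progression-free". A log-rank test "will be performed to test the difference in survival between groups", followed by Cox regression. It mentions neither the exact test, nor the cut-off of 9, nor the missing-scan rule.

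Two other places bear on this. Section 11.1.6 gives a different censoring date: "Participants alive without disease progression are censored at date of last disease evaluation". Section 13.9.2 says: "All the analyses will be conducted separately by each cohort".

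**The concern.** A participant who leaves before week 12 without a scan is a failure in 13.1 and a censored observation in 13.6. Censoring assumes that such a participant has the same outlook as those who remain. Participants who stop for toxicity or symptomatic deterioration may well do worse, so the censored estimate would tend to be too high. In a cohort of 19, one participant can settle acceptance, and the plan leaves open which 12-week rate is reported as the primary result.

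Two lesser conflicts sit in the same section. The interval level does not correspond to the level of the test. The between-group tests do not address the one-sample question and, if the groups are the three histology arms, they contradict the separate-cohort statement in 13.9.2.

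**Working it through.** **Inputs.** From 13.2: n = 19, null 0.30, alternative 0.60, cut-off 9, one-sided 10%. From 13.1: missing 12-week scan = failure. From 13.6: 90% interval and censoring at last contact. From section 11.1: scans every 6 weeks. The documents give no rate of missing 12-week scans, so the numbers lost below are assumptions.

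**1. The plan's own figure.** With X binomial on 19:
- P(X ≥ 9 | 0.30) = 0.0839, within the 10% limit. A cut-off of 8 would give 0.182.
- P(X ≥ 9 | 0.60) = 0.9115, which reproduces the stated 91%.

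**2. Count against censored estimate.** Assume 8 participants confirmed progression-free at week 12, 4 progressions at the week-6 scan, 4 at the week-12 scan, and 3 lost after week 6.
- Rule in 13.1: 8/19 = 42.1%, below 9/19 = 47.4%, so not accepted.
- Kaplan-Meier: 15 of 19 pass week 6. The 3 lost are then removed, leaving 12 at risk, of whom 8 pass week 12. The estimate is (15/19) × (8/12) = 52.6%, with a Greenwood 90% lower limit of 32.2%.

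Holding the 8 confirmed successes fixed, with losses after week 6 and progressions split as evenly as possible between the two scans:

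| Lost | Progressions (week 6 + week 12) | 13.1 rate | Kaplan-Meier |
|---|---|---|---|
| 0 | 11 (5 + 6) | 42.1% | 42.1% |
| 1 | 10 (5 + 5) | 42.1% | (14/19) × (8/13) = 45.3% |
| 2 | 9 (4 + 5) | 42.1% | (15/19) × (8/13) = 48.6% |
| 3 | 8 (4 + 4) | 42.1% | (15/19) × (8/12) = 52.6% |

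The timing of loss matters too. With 3 lost and censored at baseline, the estimate is 8/16 = 50.0%.

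**3. Interval against test.** A one-sided 10% test corresponds to a two-sided 80% interval; a two-sided 90% interval corresponds to one-sided 5%. Clopper-Pearson limits are the a/2 quantile of Beta(x, n − x + 1) and the 1 − a/2 quantile of Beta(x + 1, n − x), where a is one minus the confidence level.
- 9/19, exact 90%: 27.4% to 68.0%, includes 30% although the rule accepts.
- 9/19, exact 80%: 31.0% to 64.2%, excludes 30% and agrees with the rule.
- 8/19, exact 80%: 26.3% to 59.2%, includes 30% and agrees with non-acceptance.
- 9/19, other 90% methods: Wald 28.5% to 66.2% includes 30%; Wilson 30.07% to 65.3% just excludes it.

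The conflict arises only at exactly 9/19, with probability 9.8% under the alternative and 5.1% under the null. If the exact 90% lower limit were read as the test, the cut-off would become 10/19, with type I error 0.033 and power 0.814.

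**4. Between-group tests.** All arms receive the same regimen and are defined by histology (section 5.1). A log-rank or Cox comparison of arms contrasts histologies. It says nothing about whether one cohort's 12-week rate exceeds 30%.

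**The case against.** The strongest reply is that the decision rule is already explicit. Section 13.2 fixes acceptance at 9 of 19 for each arm, 13.1 defines every failure, and 13.9.3 likewise treats unknown response status as treatment failure. Section 13.6 states no success criterion and does not name Kaplan-Meier, which appears in 13.1 and 13.7. Its censoring sentence can be read as governing only the PFS time variable. This stands as far as the decision goes. A reader might infer that 13.6 reverses the conclusion, but the documents do not support that: in the example the plan's answer at 8/19 remains non-acceptance. It does not remove the conflict over what is reported, because 13.6 is headed as the primary analysis while 13.7 separately covers time-to-event PFS.

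The example is also constructed. Section 5.1 keeps restaging on schedule when treatment is delayed, and 5.6 asks for off-treatment scans every 8 weeks where possible. Both should limit missing scans, though neither guarantees one at week 12. The three losses are therefore an illustration, not a forecast. In the example the censoring dates in 11.1.6 and 13.6 may coincide, so the effect of that difference alone is not quantified.

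A 90% interval may properly be reported beside a one-sided 10% test if nobody reads it as the test. It would be too strong to say that the interval always contains the null at the boundary, since that depends on the unnamed method.

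Finally, 13.6 does not define its groups, and 13.5 speaks of participant groups in general. Subgroups within a cohort would be compatible with 13.9.2. On any reading, log-rank and Cox tests cannot overturn a one-sample count.

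**Conclusion.** The contradiction is real and lies in the primary-analysis section. The same participant is a failure under 13.1 and censored under 13.6, and 13.6 omits the test on which the design rests. The consequence is a reported 12-week rate that can exceed the decision rate: 52.6% against 42.1% under the assumed three losses, 45.3% against 42.1% with one loss, and no difference with none. Acceptance changes only if someone uses the censored estimate for it, which the plan neither prescribes nor excludes. The interval mismatch is narrower: it concerns only a result of exactly 9/19, and holds for the exact and Wald methods but not for Wilson. The between-group tests are misplaced in 13.6 and, if they compare the arms, conflict with 13.9.2.

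**What to change.** In 13.6, state for each cohort:
- the number progression-free under the 13.1 rule, with a missing 12-week scan counted as failure;
- the denominator: all participants in the intent-to-treat set of 13.9.2, noting that 4.1 cancels registrations of participants who receive no therapy, and reconciling this with the all-eligible wording in 13.9.3;
- the exact one-sided test with the 9-of-19 cut-off;
- an exact 80% two-sided interval, whose lower end is the one-sided 90% limit. Any 90% interval should name its method and be labelled descriptive.

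Move censored PFS to 13.7 as a secondary analysis, using the censoring date of 11.1.6. Remove the between-group log-rank and Cox tests from 13.6. Any kept in 13.7 should be labelled exploratory, with the groups defined; deleting them altogether is not necessary.

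The cost is wording only. Sample size, data collection, the type I error of 0.084 and the power of 0.912 are unchanged. The one downside is that the reported 12-week rate may be slightly lower than a censored estimate would be.
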